2.6.1.3 Time to onset of the first episode of diarrhoea

The time to onset (in days) of the first episode of diarrhoea of any grade of severity will be derived as ((date of first episode of diarrhoea – date of first dose of lapatinib and capecitabine) + 1) and it will be summarised by treatment group using Kaplan-Meier methods. Subjects who complete the study or withdraw prematurely without experiencing an episode of diarrhoea will be censored at the date of withdrawal or study completion.

The Kaplan-Meier estimate of the proportion of subjects experiencing an episode of diarrhoea will be presented for each 3 week cycle of lapatinib and capecitabine by treatment group. Estimates and 95% confidence intervals for the 25th percentile, median and 75th percentile will be provided by treatment group.

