#### **7.1.5. One Week after the First Dose of Octreotide LAR (Subjects Randomised to Receive Octreotide only)**

These assessments and procedures are to be performed 7 days after the first dose of octreotide LAR in subjects randomised to receive octreotide only.

- Record any AEs and SAEs and assign appropriate toxicity grade (NCI CTCAE, version 4.03).
- Dermatological examination, if clinically indicated.
- FACIT-D questionnaire and the baseline DMD. These must be completed before the first dose of lapatinib and capecitabine.
- Record all concomitant medications added and/or changed.
- Record visits to/contact with healthcare professionals associated with diarrhoea AEs.
- Record intravenous rehydration associated with diarrhoea AEs.
- Dispense lapatinib and capecitabine to the subject with instructions for taking therapy.

Other assessments, such as haematology, clinical chemistry, liver function tests and change in disease status should be conducted in accordance with the local standard of care. Liver function tests and change in disease status should be recorded as required in the relevant modules of the eCRF. Haematology and other clinical chemistry tests should be recorded in the eCRF only if associated with an AE or SAE.

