#### **7.4.7. Time Period and Frequency of Detecting AEs and SAEs**

The investigator or site staff is responsible for detecting, documenting and reporting events that meet the definition of an AE or SAE.

AEs will be collected from the time of treatment with the first dose of octreotide for subjects randomised to receive octreotide and treatment with the first dose of lapatinib and capecitabine for subjects randomised to receive no octreotide until 30 days following the end of the 24 week study period or discontinuation of study-related treatment, whichever is sooner, regardless of initiation of a new cancer therapy or transfer to hospice.

Serious AEs will be collected over the same time period as stated above for AEs. In addition, any SAE assessed **as related** to study participation (e.g., protocol-mandated procedures, invasive tests, or change in existing therapy), study treatment or GSK concomitant medication must be recorded from the time a subject consents to participate in the study up to and including any follow-up contact. All SAEs will be reported to GSK within 24 hours, as indicated in Section 7.4.9.

Serious AEs, AEs of special interest, AEs leading to treatment discontinuation and pregnancies will be collected for all subjects who enter the LTFU phase of the study (Section 7.1.9).

After discontinuation of study treatment, the investigator will monitor all AEs/SAEs that are ongoing until resolution or stabilization of the event or until the subject is lost to follow-up. At any time after 30 days the investigator may report any AE that they believe possibly related to study treatment.

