1.1 Study design

This is a randomised, parallel group, multi-centre, open-label Phase II study in subjects with HER2-positive metastatic breast cancer which has progressed following prior therapy, which must have included anthracyclines and taxanes and therapy with trastuzumab in the metastatic setting. This study is not placebo controlled, and there is no active comparator.

Subjects must be screened for eligibility and informed consent must be given before any study-related procedures are conducted.

All subjects will receive treatment with lapatinib 1250mg once daily and capecitabine 1000mg/m² twice daily until disease progression. Lapatinib will be given every day; capecitabine will be given in 3 week cycles of two weeks treatment followed by one week off treatment. All subjects with episodes of diarrhoea will be encouraged to follow the diarrhoea management guidelines for subjects receiving lapatinib. One cycle of lapatinib and capecitabine equates to three study weeks.

Subjects will be randomised in a 1:1 ratio to receive either:

- Octreotide (Sandostatin long acting release (LAR)) 40mg 7 days before the start of treatment with lapatinib and capecitabine and again 28 days later, or

- No octreotide treatment.

For subjects randomised to receive octreotide, treatment with lapatinib and capecitabine will be initiated 7 days after the first dose of octreotide given as the LAR formulation. For subjects randomised to receive no octreotide, treatment with lapatinib and capecitabine will be initiated immediately following enrolment.

Subjects randomised to receive octreotide LAR must be given one 0.1mg dose of the standard formulation of octreotide subcutaneous (s.c.) to assess tolerability at least one hour before the first dose of the LAR formulation is administered. Subjects with significant intolerance to octreotide 0.1mg s.c. will not receive treatment with octreotide LAR, but will receive treatment with lapatinib and capecitabine as scheduled.

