2.5.2 Statistical hypothesis, model, and method of analysis

2.5.2.1 Diarrhoea of Grade 2 and above during the first 3 cycles treatment

This study is designed to test the superiority of prophylactic octreotide vs. no prophylactic octreotide in reducing the proportion of subjects experiencing diarrhoea with a severity of 2 or higher during the first 9 weeks (i.e., 3 cycles treatment) of lapatinib and capecitabine. Superiority will be assessed using data from the Intent-to-Treat population. The following statistical hypothesis will be tested to address the primary efficacy objective:

$$H_0: \delta = 0 \text{ vs. } H_a: \delta < 0,$$

where δ is the difference in the incidence of Grade 2 or higher diarrhoea between prophylactic vs. no prophylactic octreotide during the first 3 cycles of lapatinib and capecitabine.

The AE term ‘diarrhoea’ will be used to select episodes of diarrhoea.

Episodes of diarrhoea ‘during the first 3 cycles of treatment’ are defined as those with an onset date on or after the efficacy reference start date as defined in [Section 2.1.3.2](#) and before the Cycle 4 visit date.

Subjects who withdraw from the study on or prior to the Cycle 4 visit date will be assumed to have experienced diarrhoea (non-responder imputation) of grade 2 or higher.

The superiority of prophylactic octreotide compared to no prophylactic octreotide will be assessed using a Pearson chi-square test in ITT population. The implementation of the Pearson chi-square test is specified in [Section 5.3.1](#). The proportion of subjects experiencing at least one episode of diarrhoea with a severity of Grade 2 or higher in each treatment group, the difference in proportions between the treatment groups, the corresponding 95% confidence interval and the two-sided p-value from the chi-square test will be presented.

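### The time-to-first-diarrhoea formula in SAP 2.6.1.3 sets no earliest onset date, so an octreotide-arm episode before lapatinib and capecitabine gets a time of −6 to 0, with no rule for handling it

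*SAP*

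**What the plan says.** SAP 2.6.1.3 takes the time in days as "date of first episode of diarrhoea – date of first dose of lapatinib and capecitabine", plus 1, and summarises it by arm with Kaplan-Meier methods. The origin in both arms is thus the "date of first dose of lapatinib and capecitabine". It uses the first episode of any grade and sets no earliest onset date. SAP 2.6.1 places the analysis in the ITT population. The protocol's account of this endpoint (9.3.5.1.2) names no time origin.

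The arms differ in what happens, and what is recorded, before that dose:

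- **Schedule (SAP 1.1).** In the octreotide arm "treatment with lapatinib and capecitabine will be initiated 7 days after the first dose of octreotide given as the LAR formulation". In the control arm "treatment with lapatinib and capecitabine will be initiated immediately following enrolment".
- **AE collection (Protocol 7.4.7).** "AEs will be collected from the time of treatment with the first dose of octreotide for subjects randomised to receive octreotide". For the control arm the start is "treatment with the first dose of lapatinib and capecitabine for subjects randomised to receive no octreotide".
- **Extra visit (Protocol 7.1.5).** AEs from the week after octreotide are recorded at a dedicated visit: "These assessments and procedures are to be performed 7 days after the first dose of octreotide LAR in subjects randomised to receive octreotide only".

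The proportion endpoints start elsewhere. SAP 2.5.2.1 counts episodes "with an onset date on or after the efficacy reference start date", which SAP 2.1.3.2 sets at randomisation. SAP 2.5.2.2 uses the same start for the whole treatment period, and 2.6.1.2 applies those methods to diarrhoea of any grade.

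**The concern.** The formula counts from lapatinib/capecitabine, but the events fed into it are not restricted to that period. Only the octreotide arm has a week of routinely collected AEs before the origin, so essentially only that arm can produce times of zero or less. A Kaplan-Meier estimate is defined on non-negative times. A subject with a negative time must be dropped, given another value, or represented by a later episode, and the SAP does not say which.

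The stated objective is a longer time to onset, and the subjects affected are the octreotide subjects with the earliest diarrhoea. Part of the description of that objective would therefore rest on a programming decision, although SAP section 1 says that all final-analysis decisions were made before database lock. The curve would also disagree with the any-grade proportion, where the same episode is an event.

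**Working it through.** **1. Dates into the formula.** Put octreotide LAR on day 0 and lapatinib/capecitabine on day 7 (SAP 1.1).

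| Onset | Onset − first lapatinib/capecitabine dose | +1 |
|---|---|---|
| Day of first LAR dose | −7 | −6 |
| Day before lapatinib/capecitabine | −1 | 0 |
| Day of first lapatinib/capecitabine dose | 0 | 1 |

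The run-in maps to −6 to 0: six negative days and one zero. In the control arm routine collection starts at the origin, so the minimum is 1. The one exception is that related SAEs are recorded from consent in both arms (Protocol 7.4.7).

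**2. Does another rule resolve it?**

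- The m-ITT population (SAP 2.2) leaves out certain octreotide-arm subjects with run-in diarrhoea, but this endpoint is analysed in ITT.
- The study-day rule (SAP 2.1.3.4) has no day 0 and adds no 1 before the reference date, so it would give −7 to −1. That differs from 2.6.1.3 and is still negative.
- SAP 5.3.2 specifies the Kaplan-Meier procedure and is silent on non-positive times.

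**3. How many subjects?** Neither document gives a run-in rate. Protocol 1.2 cites diarrhoea in more than 10% of octreotide patients, usually after the first dose, but not for this week. Protocol 3.2 says concentrations may be too low to cause AEs in the first 7 days. I assume q = 5, 10 or 15%. The 62 enrolled subjects (SAP section 1) under 1:1 allocation give about 31 per arm.

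| q | Expected, 31q | P(at least one), 1 − (1 − q)^31 |
|---|---|---|
| 5% | 1.6 | 80% |
| 10% | 3.1 | 96% |
| 15% | 4.7 | 99% |

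**4. What dropping would do.** Let f be the octreotide-arm proportion with any episode, run-in included, with no censoring. Dropping run-in subjects reports (f − q)/(1 − q). As illustrative values of f, 45% and 65% are the any-grade rates that Protocol 1.1 cites for lapatinib with capecitabine in EGF111438 and in the published EGF100151 data.

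| f | q = 5% | q = 10% | q = 15% |
|---|---|---|---|
| 45% | 0.40/0.95 = 42% | 0.35/0.90 = 39% | 0.30/0.85 = 35% |
| 65% | 0.60/0.95 = 63% | 0.55/0.90 = 61% | 0.50/0.85 = 59% |

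**5. Against which reference?** The figures in step 4 are shortfalls from f, which counts every episode. Suppose instead that only onsets from the first lapatinib/capecitabine dose count, and that a share r of run-in subjects has a later new episode. The proportion is then f − q + qr. For f = 45% and q = 10%:

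| r | Onsets from lapatinib/capecitabine only | Run-in subjects dropped |
|---|---|---|
| 0 | 35% | 38.9% |
| 38.9% | 38.9% | 38.9% |
| 100% | 45% | 38.9% |

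Dropping understates diarrhoea relative to this reference only if run-in subjects have later diarrhoea more often than the others. If less often, it overstates it. Resetting negative times to 1 would keep the full 45% but place the run-in events on day 1.

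**The case against.** The strongest reply is that only one clause is missing. The origin is already common to both arms and suits a question about diarrhoea on lapatinib plus capecitabine. That stands: a reader might infer that the arms are timed from different starting points, and the text does not say so. What is missing is the limit on eligible onset dates.

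A reader might also infer that these subjects will be removed and that the result will favour octreotide. The documents do not support that. Neither says that subjects are dropped, a time of exactly 0 is usable, and step 5 shows that the direction depends on the reference analysis and on recurrence. The inputs are also soft: the rate above 10% is not specific to this week, and the 45% comes from patients without octreotide.

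Nor are run-in episodes hidden. SAP 2.6.1.2 lists every diarrhoea event with its time to onset, and the any-grade proportion counts from randomisation. The consequences are small: a secondary summary in an abbreviated report, after a futility stop, without the log-rank comparison that the protocol had planned.

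These replies limit the size of the point and rule out a general claim of bias. They do not supply a rule for the negative times, and the listing's own time-to-onset column inherits the problem.

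**Conclusion.** The point holds as a defect in the derivation. As written, SAP 2.6.1.3 gives unusable times for most run-in onsets, essentially in one arm, and no other section resolves them. It also conflicts with the any-grade proportion on whether such an episode counts.

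The size is conditional. With 5/10/15% of the octreotide arm dropped, 45% would read 42/39/35%. This assumes those run-in rates, no censoring, run-in episodes contained within the 45%, and comparison with an all-episode analysis. No direction can be claimed against an analysis restricted to onsets on lapatinib and capecitabine. Nothing here changes the primary result or the futility decision. The effect is confined to a descriptive secondary endpoint with no planned test.

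**What to change.** In SAP 2.6.1.3, keep the existing origin and add one sentence: the event is the first episode with onset on or after the first dose of lapatinib and capecitabine, in both arms. All event times are then at least 1, and no subject is lost because of a run-in episode.

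Add a small table of octreotide-arm episodes with onset between the first octreotide dose and the first lapatinib/capecitabine dose. As a sensitivity analysis, time from randomisation with all episodes counted, which matches the start used for the any-grade proportion. State how the listing in 2.6.1.2 shows time to onset for run-in episodes.

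The cost is one sentence, one short table and one repeat of an existing program, with no new data.

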**9.3.5.1.2. Secondary endpoint analysis: Investigator-reported endpoints**

These analyses will be based on data reported by the investigator in the eCRF. Analyses of secondary diarrhoea-related endpoints will be conducted for the ITT and m-ITT populations using the same lapatinib and capecitabine treatment intervals as described for the analysis of the primary endpoint in Section 9.3.5.1.1. Disease efficacy will be assessed in the ITT and m-ITT populations over the total 24 week treatment period. For the secondary endpoints, 95% confidence intervals and two-sided tests will be presented.

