**Time to onset of the first episode of diarrhoea**

The time to onset of the first episode of diarrhoea of any grade of severity will be summarised by treatment arm using Kaplan-Meier methods. Subjects who complete the study or withdraw prematurely without experiencing an episode of diarrhoea will be censored at the date of withdrawal or study completion. The Kaplan-Meier estimate of the proportion of patients experiencing an episode of diarrhoea will be presented for each 3-week time interval by treatment group. Estimates and 95% confidence intervals for the 25th percentile, median and 75th percentile will be provided by treatment group. Treatment groups will be compared using the log-rank test, or the Wilcoxon test in the case of non-proportional hazards.

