To determine the efficacy of prophylactic octreotide in reducing the proportion of subjects experiencing diarrhoea of any grade of severity.	Proportion of subjects experiencing diarrhoea of any grade of severity as defined by the NCI-CTCAE, version 4.03, recorded as AEs in the eCRF.
To determine the efficacy of prophylactic octreotide in increasing the time to onset of the first episode of diarrhoea of any grade of severity.	Time to onset of the first episode of diarrhoea of any grade of severity, recorded as an AE in the eCRF.

Objectives	Endpoints
Secondary: Investigator reported	
To determine the effect of prophylactic octreotide on compliance with lapatinib and capecitabine treatment.	Number of lapatinib and capecitabine tablets dispensed and returned, recorded in the eCRF.
To determine the effect of prophylactic octreotide on the efficacy of treatment with lapatinib and capecitabine.	Overall response rate and clinical benefit response measured in accordance with the Response Evaluation Criteria In Solid Tumours (RECIST) version 1.1.
To determine the effect of prophylactic octreotide on the safety and tolerability of cancer treatment.	Proportion of subjects with AEs and SAEs, recorded in the eCRF.
Secondary: Patient reported Diarrhoea Management Diary (DMD)	
To determine the effect of prophylactic octreotide on patient reported diarrhoea.	Patients reporting changes in bowel movements from baseline (frequency and/or consistency), recorded in the DMD.
Quality of Life – FACIT-D	
To determine the effect of prophylactic octreotide on health-related quality of life.	Trial Outcomes Index will be the primary measure; the sub-scales, Total FACT-G score and Total FACIT-D score will be secondary measures.

2 Statistical methods

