3.3 Sample Size Re-estimation

Sample size re-estimation is not planned for this study.

4 Change to protocol specified analyses

Since final CSR will be an abbreviated CSR, not all endpoints will be analysed. [Table 1-3](#) contains reduced list of endpoints as compared to protocol.

Secondary endpoint Patient reported Diarrhoea Management Diary (DMD) is reported using a listing of patients reporting changes in bowel movements from baseline (frequency and/or consistency), recorded in the DMD.

5 Appendix

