5.3.2 Analysis of time to events data

Kaplan-Meier estimates

An estimate of the survival function in each treatment group will be constructed using Kaplan-Meier (product-limit) method as implemented in PROC LIFETEST with METHOD=KM option. The PROC LIFETEST statement will use the option CONFTYPE=LOGLOG.

25th, 50th, and 75th percentile survivals for each treatment group will be obtained along with 95% confidence intervals calculated from PROC LIFETEST output using the method of [Brookmeyer and Crowley 1982]. Kaplan-Meier estimates of the survival function with 95% confidence intervals at specific time points will be summarized.

Treatment of ties

The STRATA statement in LIFETEST procedure will be used to analyze time to event data with ties.

6 Reference

1. Agresti, A. A Survey of Exact Inference for Contingency Tables. *Statistical Science*, 1992; 7(1),131–177.
5. Carroll KJ. Back to basics: Explaining sample size in outcome trials, are statisticians doing a thorough job? *Pharmaceutical Statistics*, 2009; 8(4):333-345.
6. Clopper CJ and Pearson ES (1934). The use of confidence or fiducial limits illustrated in the case of the binomial. *Biometrical*, 26, 404-413.
7. Santner, T. J. and Snell, M. K., Small-Sample Confidence Intervals for p_1-p_2 and p_1/p_2 in 2 X 2 Contingency Tables. *Journal of the American Statistical Association*, (1980; 75, 386–394.

8. Schuirmann DJ. A comparison of the two one-sided tests procedure and the power approach for assessing the equivalence of average bioavailability. *Journal of Pharmacokinetics and Biopharmaceutics*, 1987; 15(6):657-80.

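### The SAP keeps the objective of delaying the first diarrhoea episode but plans no between-arm comparison for it, and its list of changes does not say so

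*SAP*

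**What the plan says.** **Objective.** SAP Table 1-3 retains, among the investigator-reported secondary objectives: "To determine the efficacy of prophylactic octreotide in increasing the time to onset of the first episode of diarrhoea of any grade of severity". The matching endpoint is kept beside it.

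**Protocol analysis.** Protocol 9.3.5.1.2 plans Kaplan-Meier summaries, quartiles with 95% confidence intervals and a comparison: "Treatment groups will be compared using the log-rank test, or the Wilcoxon test in the case of non-proportional hazards". The same section sets the general rule: "For the secondary endpoints, 95% confidence intervals and two-sided tests will be presented". It names no hazard ratio for this endpoint.

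**SAP analysis.** SAP 2.6.1.3 defines the onset time and states that "it will be summarised by treatment group using Kaplan-Meier methods". It censors event-free subjects at withdrawal or completion, and reports Kaplan-Meier proportions for each 3-week cycle. It adds: "Estimates and 95% confidence intervals for the 25th percentile, median and 75th percentile will be provided by treatment group". It stops there. SAP 5.3.2 gives the software details for Kaplan-Meier estimates, with confidence intervals for percentiles and at specific time points. Its only other instruction concerns ties: "The STRATA statement in LIFETEST procedure will be used to analyze time to event data with ties".

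**Record of changes.** SAP Section 4 says "Since final CSR will be an abbreviated CSR, not all endpoints will be analysed", notes that Table 1-3 "contains reduced list of endpoints as compared to protocol", and explains that the diary endpoint becomes a listing. The SAP Introduction says in general terms that the abbreviated report will carry fewer analyses than the protocol planned.

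**The concern.** Increasing the time to onset is a comparative objective: octreotide against no octreotide. Every output specified for it describes one arm at a time. The report will let a reader look at two sets of estimates, but it will give no difference, ratio, interval for the effect or test.

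After a futility stop, the useful question about a secondary efficacy objective is what size of effect the data still allow. Only an interval on the contrast answers that. Without one, readers will compare medians or curves by eye, or make their own calculation.

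The change is also hard to trace. Time to onset was not removed from the endpoint list, so the explanation in SAP Section 4 does not cover it. A reader cannot tell whether the comparison was dropped on purpose or lost in editing.

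**Working it through.** **1. The texts side by side**

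| Element | Protocol 9.3.5.1.2 | SAP 2.6.1.3 and 5.3.2 |
|---|---|---|
| Kaplan-Meier proportion per 3 weeks, by arm | yes | yes |
| Quartiles with 95% CI, by arm | yes | yes |
| Censoring at withdrawal or completion | yes | yes |
| Between-arm test | log-rank, or Wilcoxon | none named |
| Effect estimate between arms | none named | none named |

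The SAP follows the protocol paragraph closely and leaves out the sentence with the test. The STRATA statement in SAP 5.3.2 does not restore it. That procedure can print a log-rank result, but the SAP brings STRATA in only under ties and plans no reported p-value.

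**2. How the SAP drops tests elsewhere**

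SAP 2.5.2.2 (Grade 2 or higher over the whole treatment period) and 2.5.4 (m-ITT and per-protocol populations) each say outright that no test will be done. SAP 2.6.1.3 has no such sentence. Protocol 9.3.5 requires deviations from its analysis plan to be documented in the analysis plan and the final report.

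**3. What a restored comparison could show**

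The plan gives no power or precision figure for this endpoint, so there is none to reproduce. Inputs:

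- 62 subjects enrolled (SAP Introduction). An even split of 31 per arm is assumed; the actual split is not given.
- Any-grade incidence on lapatinib plus capecitabine of 45% (EGF111438, protocol Table 3) and 69% (EGF100151, protocol Table 2). These are assumed to hold for the control arm.
- A true hazard ratio of 0.5, chosen for illustration.
- Two-sided alpha of 0.05.

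Under proportional hazards, octreotide-arm incidence is 1 − (1 − p)^0.5, where p is control incidence.

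- p = 0.45: 1 − 0.55^0.5 = 0.258. Events = 31 × (0.45 + 0.258) ≈ 22.
- p = 0.69: 1 − 0.31^0.5 = 0.443. Events = 31 × (0.69 + 0.443) ≈ 35.

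Power (Schoenfeld, equal allocation) = Φ(√(D/4) × ln 2 − 1.96), where D is the number of events.

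- D = 22: Φ(2.345 × 0.693 − 1.96) = Φ(−0.33) ≈ 37%.
- D = 35: Φ(2.958 × 0.693 − 1.96) = Φ(0.09) ≈ 54%.

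The approximate 95% CI for the hazard ratio is the estimate divided and multiplied by exp(1.96 × 2/√D).

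- D = 22: exp(3.92/4.690) ≈ 2.3. An estimate of 0.5 would carry an interval of about 0.22 to 1.15.
- D = 35: exp(3.92/5.916) ≈ 1.9. An estimate of 0.5 would carry an interval of about 0.26 to 0.97.

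Applying the historical incidence to all 62 subjects would give 28 to 43 events. That count goes with no treatment effect and should not be paired with a hazard ratio of 0.5.

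The event counts may still be too high. The source incidences are not cut at 24 weeks; onset in EGF111438 ran to day 411 (protocol Table 4).

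**The case against.** The best defence is that the reduction was announced and is reasonable. The trial stopped for futility, the SAP says the abbreviated report will contain fewer analyses, and SAP 5.1 provides for a study-team review of which analyses remain appropriate if the study is terminated. Making secondary endpoints descriptive fits the rest of the SAP, and an underpowered p-value adds little. The protocol promised only a test, so a hazard ratio is a new analysis, added after the interim result was known.

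Much of this stands. Reducing the analyses is legitimate, the practical impact is modest, and the hazard ratio must be labelled as an addition. But a general notice does not identify this change or supply a contrast for an objective the SAP chose to keep. Low power argues against relying on the p-value; it is a reason to give an interval.

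Stronger readings that the documents do not support:

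- **That nothing useful will be reported.** Cycle-by-cycle proportions, quartiles with intervals and a by-subject listing of onset times remain. A rough difference could be worked out from the two arms' estimates. What is missing is a planned and reported contrast.
- **That this is the only ITT diarrhoea analysis that does not count withdrawals as events.** SAP 2.5.3 also applies no imputation to Grade 2 or higher diarrhoea over the entire treatment period.
- **That it is a direct check on the primary result.** It concerns any-grade diarrhoea up to 24 weeks; the primary endpoint is Grade 2 or higher in the first three cycles.
- **That the protocol's Wilcoxon fallback inflates type I error by a known amount.** The protocol makes the fallback conditional on non-proportional hazards, without giving a criterion. It does not say to take the smaller p-value, and the SAP contains no switch at all.

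**Conclusion.** The point holds. A comparative secondary objective is retained, its only planned between-arm analysis has gone without an itemised record, and nothing replaces it. This is a gap in one secondary endpoint and in the change record. It does not affect the primary analysis or the futility decision.

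The textual finding needs no assumptions. The precision figures (about 22 to 35 events, 37% to 54% power, an interval factor of about 2.3 to 1.9) rest on an even split of 62 subjects, historical incidence carried over to the control arm, proportional hazards and an illustrative hazard ratio of 0.5. They show that a non-significant result would say little and that only a large effect could be seen clearly.

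**What to change.** In SAP 2.6.1.3:

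- Add a Cox hazard ratio (octreotide against no octreotide) with a 95% CI.
- Restore the log-rank test, two-sided, as the single named test.
- Optionally, add the between-arm difference in Kaplan-Meier incidence at the end of cycle 3 with a 95% CI.
- Label all of these secondary, unadjusted for multiplicity and descriptive.

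In SAP Section 4, record that the hazard ratio (and the difference, if used) is an addition made after the interim result was known, and that the protocol's Wilcoxon fallback is removed.

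If the team prefers no comparison, the minimum is to state in 2.6.1.3 and Section 4 that the protocol's test is dropped and the endpoint is descriptive only. That closes the documentation gap but leaves the objective without an effect estimate.

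The cost is a few lines of code and a table row on data already being analysed. The downside is one more imprecise, unadjusted secondary result that could be over-read.
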